5.4 Risks and Anticipated Adverse Device Effects That Are to Be Assessed

The risks and anticipated adverse device effects (ADE) are summarized in Section 14.6 as well as the IB. All ADEs will be assessed by collection of adverse events which will be determined by the investigator as either being related to the device or not.

6 DESIGN OF THE CLINICAL INVESTIGATION

6.1 General

6.1.1 Description of Trial

The JNIR Trial will enroll approximately 100 subjects with a wide spectrum of PCI indications (stable angina as well as ACS, including subacute STEMI (>72 hours since first hospital presentation).

This is a prospective, multi-center, single-arm, open label clinical trial. Lesions planned to be treated must be declared and recorded at time of enrollment.

6.1.2 Rationale for Trial

Drug eluting stents have significantly lowered the restenosis rate following PCI. Because of delayed re-endothelization, however, prolonged (current recommendations are for 12 months) dual anti-platelet therapy (DAPT) is indicated, but has not completely eliminated stent thrombosis, a serious complication with potential mortality. Rates for stent thrombosis with

second generation DES have been in the range of 1-3% at one year after stent implantation. Rates for restenosis as well as ST vary between stents and depend on a myriad of factors including stent design (for example, open- vs. closed-cell), strut thickness, stent material, flexibility of the stent, and degree of mal-apposition. It is therefore important to evaluate new stents.

The present trial is therefore aimed at assessing TLF at one year with the MedJ-01 stent in a Japanese patient population to show non-inferiority of JNIR01 Target Lesion Failure at 12 months (TLF_{12}) to the BIONICS TLF_{12} .

The rationale for selection of TLF as the primary endpoint is based on recent US trials of best in class DES (Xience V, Promus Element and Resolute) including SPIRIT III, SPIRIT IV, PLATINUM, RESOLUTE US, RESOLUTE ALL-COMERS, TWENTE, COMPARE, and COMPARE II.

6.1.3 **Primary and Secondary Endpoints**

6.1.3.1 Primary Endpoint

The primary endpoint is Target Lesion Failure (TLF) at 12 months defined as the composite of cardiac death, target vessel-related myocardial infarction (MI), or ischemia-driven target lesion revascularization (TLR).

Definitions of terms and endpoints are located in Section 21.1. Acronyms and abbreviations are defined in Section **Error! Reference source not found.**

6.1.3.2 Clinical Secondary Endpoints

The secondary endpoints are to be evaluated at 30 days, 6 months, and 1, 2, 3, 4, and 5 years except as noted:

- Device, Lesion, and Procedure Success at time of baseline procedure
- TLF at 30 days, 6 months, and 2, 3, 4, and 5 years defined as the composite of cardiac death, target vessel-related MI, or ischemia-driven TLR.
- Major adverse cardiac events (MACE; the composite rate of cardiac death, any MI or ischemia-driven TLR)
- Target vessel failure (TVF; the composite rate of death, target vessel related MI or ischemia-driven TVR)
- All-cause mortality
- Cardiac death
- Myocardial infarction
- Target vessel related MI
- Ischemia-driven TLR
- Ischemia-driven TVR
- Stent thrombosis (ARC definite and probable)

6.1.4 Methods and Timing for Assessing, Recording, and Analyzing Variables

Data collection commences after the subject has provided informed consent. Data collection including subject demographic information, laboratory tests, and procedural data as well as follow-up visits or telephone contacts will be conducted by an Investigator or site coordinator who has been trained on the CIP and Case Report Forms (CRF).

Data required for analysis will be obtained as outlined in Table 3.

After discharge from the hospital, each subject will be followed with in-clinic or phone followup visits at 30 days, 6 months, and 1, 2, 3, 4, and 5 years. The 1-year follow-up will be conducted in-clinic unless the patient refuses to or cannot come to clinic.

TYPE OF DATA TO BE COLLECTED	Screening (within 7 days ¹)	Pre-Procedure (within 24 hours)	Baseline Procedure	Post-Procedure	30 days (± 7 days)	6 Months (± 30 days)	1 year (-30 days / +14 days) ²	2 years (± 60 days)	3 year (± 60 days)	4 year (± 60 days)	5 year (± 60 days)	Unscheduled visits
Patient Informed Consent	✓											
Patient Medical/Clinical History	✓											
Angina Status	✓	✓		✓	✓	✓	✓	✓	✓	✓	✓	✓
General Eligibility Criteria	~											
Angiographic Eligibility Criteria			~									
Clinical Laboratory Tests:												
Pregnancy Test (childbearing potential women only)	~											
CBC, Creatinine, BUN	✓											
Lipid profile ³	✓											
CK, CK-MB or Troponin		\checkmark^4		√ ⁵								√ ⁶
12-Lead ECG		<		~			✓ ²					✓ ⁶
Coronary Angiogram & PCI			✓									
Enrollment and Study Stent Information			~									
Per Protocol DAPT Medications ⁷		✓	✓	✓	~	✓	✓					
DAPT Medications								√	√	✓	✓	√
Concomitant Cardiac Medications ⁸		~		~	*	~	~	1	~	1	~	~
Adverse Events Monitoring		√ ⁹	✓	✓	✓	✓	✓	✓	√	✓	✓	✓

Table 3: Schedule of Data Collection

1. Subjects who undergo angiography following screening within 7 days but cannot proceed directly to enrollment (ie, undergo target PCI) can be enrolled within 30 days of the initial screening without reconsenting the patient and repeating screening procedures unless clinically indicated. 24 hr preprocedure angina status, cardiac enzymes, and ECG need to be repeated. In cases where target PCI is performed within 24-72 hrs. from non-target PCI, serial enzymes need to be obtained as detailed in inclusion criteria 3c.

2. In-clinic visit at 1-year follow-up and ECG may be waived if subject refuses to return to clinic or is unable to return. A telephone visit should then be conducted in lieu of a clinic visit.

3. Lipid profile is strongly recommended.

- 4. Within 24 hours pre-procedure. For subjects with ACS, enzyme levels need to be within 8 hours of the procedure or have already been shown to be decreasing. For subacute STEMI patients enzyme levels must have peaked for either CK-MB or Troponin (I or T) or both. High sensitivity troponin assays (hsTrop) are acceptable if non-hsTrop and CK-MB are not available at the local hospital.
- 5. If Troponin is elevated or CK-MB is elevated ≥ upper limit of normal, serial measurements of CK and CK-MB (preferred) or Troponin (I or T) must be done until a decline is noted
- 6. CK and CK-MB or Troponin (I or T) and ECG should be obtained for all suspected ischemic events. CK-MB is preferred but at sites where CK-MB is not available Troponin I or T may be used.
- 7. Clopidogrel 75 mg daily or prasugrel 2.5 to 3.75 mg daily must be given for a minimum of 12 months according to national guidelines and standard of care as well as aspirin 81 to 100 mg daily to be taken indefinitely.
- 8. Concomitant cardiac medications will be recorded by categories (e.g., statin, non-statin lipid lowering, ACE inhibitors, ARBs, beta-blockers, calcium channel blockers, other anti-anginals).
- 9. Adverse events that occur after informed consent has been obtained will be recorded.

6.1.4.1 Screening and Pre-Procedure

Subject preparation will occur in accordance with standard hospital policy for the care of interventional cardiology patients. Once screening has determined that a patient meets the general inclusion and exclusion criteria, written informed consent will be obtained according to Section 13.

Subject information will include the following. Refer to Section 21.1 for definitions.

- Demographics (e.g., age, gender, height, weight)
- Risk factors (dyslipidemia, hypertension, family history of premature coronary disease, tobacco use, alcohol use and diabetes)
- Cardiac history (previous MI, intervention history, and past angina status according to CCS and Braunwald classifications)
- Current angina status
- General eligibility criteria
- Per-protocol DAPT medications
- Concomitant cardiac medication by category
- Adverse events that occur after informed consent has been obtained
- Assurance that informed consent has been obtained correctly

Subjects who undergo angiography following screening within 7 days but cannot proceed directly to enrollment (i.e., undergo target PCI) can be enrolled within 30 days of the initial screening without reconsenting the patient and per the following:

- Repeating screening procedures is not required, unless clinically indicated.
- 24 hr. pre-procedure angina status, cardiac enzymes, and ECG need to be repeated.
- In cases where target PCI is performed within 24-72 hrs. of non-target PCI, serial enzymes need to be obtained as detailed in inclusion criteria 3c.

6.1.4.2 **Pre-Procedure Laboratory Assessments**

The following laboratory assessments are to be performed or must be available (having been done as part of routine clinical care) prior to the baseline procedure.

Required within 7 days prior to procedure:

- Complete Blood Cell Count (CBC): RBC, WBC, hemoglobin, hematocrit, platelet
- Creatinine, BUN

Calculated creatinine clearance <30 mL/min using Cockcroft-Gault equation:

- Male: $Ccr = \{(140 age) x weight (kg)\}/\{72 x serum creatinine level (mg/dL)\}$
- Female: $Ccr = 0.85 x \{(140 age) x weight (kg)\}/\{72 x serum creatinine level (mg/dL)\}$
- Pregnancy test (if applicable)

If following angiography non-target PCI is performed but the subject cannot proceed directly to enrollment (ie, perform target PCI) the subject may be enrolled within 30 days of the initial screening without repeating the above tests.

Strongly recommended within 7 days prior to procedure:

• Lipid profile (total cholesterol, LDL, HDL, triglycerides)

If following angiography non-target PCI is performed but the subject cannot proceed directly to enrollment (i.e., perform target PCI) the subject may be enrolled within 30 days of the initial screening without repeating the above tests.

Required within 24 hours pre-procedure:

- Electrocardiogram (ECG) (See the trial's Site Binder for ECG Core Lab Guidelines)
- Current angina status
- Creatine kinase (CK) and creatine kinase muscle-brain isoenzyme (CK-MB) (For subjects with ACS, enzyme levels need to be within 8 hours of the procedure or have already been shown to be decreasing.)
- Troponin (T or I) where CK-MB is not available
- If following angiography non-target PCI is performed but the subject cannot proceed directly to enrollment (i.e., perform target PCI) the subject may be enrolled within 30 days of the initial screening BUT THE ABOVE WITHIN 24 HR PROCEDURES MUST BE REPEATED WITHIN 24 HRS. OF ENROLLMENT.

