- 23. Patient is participating in any other investigational drug or device clinical trial that has not reached its primary endpoint or plans to participate in any clinical trial.
- 24. Women who are pregnant or breastfeeding (women of child-bearing potential, defined as females of childbearing potential if they have not undergone a permanent contraceptive operation or they are not postmenopausal, must have a negative pregnancy test within one week before treatment. Permanent contraceptive operation is defined as: hysterectomy, hysterosalpingectomy, or bilateral oophorectomy. The status of a female should be

considered as postmenopausal when she has not had a period for 12 consecutive months without an alternative medical cause).

- 25. Women who intend to procreate within 12 months after the baseline procedure (women of child-bearing potential who are sexually active must agree to use a reliable method of contraception from the time of screening through 12 months after the baseline procedure).
- 26. Patient has received an organ transplant or is on a waiting list for an organ transplant.
- 27. Patient is receiving or scheduled to receive chemotherapy within 30 days before or any time after the baseline procedure.
- 28. Patient is receiving oral or intravenous immunosuppressive therapy or has known lifelimiting immunosuppressive or autoimmune disease (e.g., HIV). Corticosteroids are allowed.

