6.3.4 Point of Enrollment

Patients will be screened and consented for enrollment prior to any sedation. Patients may be consented prior to diagnostic angiography with possible PCI intervention as well as prior to a planned PCI procedure. Once a patient has signed an informed consent, met all general and angiographic eligibility criteria, and a guidewire has successfully been passed beyond the target lesion, the patient will be considered enrolled in the trial (refer to instructions for deregistration in the trial's Site Binder). If the study stent could not be implanted due to reasons that are not related to study device,, the study subject will be de-registered from the trial and will not be analyzed as part of the full analysis set (FAS).

The screening and enrollment process is displayed in Figure 5 Error! Reference source not found.

^{*:} refer to 6.4.3 Enrollment

Figure 5: Screening and Enrollment Flow Chart

The trial will enroll patients for whom a decision to undergo PCI has already been made. In the case CABG-eligible conditions, it is recommended that a heart team be consulted in the decision of whether the patient should undergo CABG or PCI.

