6.3. PER PROTOCOL SET [PPS]

The Per Protocol Set (PPS) will contain all patients who receive the study stent with no major protocol violations. Major protocol violations include enrollment of a patient:

- · whose informed consent was not properly obtained
- who did not meet all of the inclusion or exclusion criteria
- who did not receive the study stent due to any reason
- who did not receive at least 12 months of Dual Antiplatelet Therapy (DAPT) post baseline procedure. Details of DAPT to be received post-procedure are given in Section 6.4.9.3 of the protocol.

Major protocol violations leading to exclusion from the PPS will be summarized using the FAS.

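### The 30-day re-screening waiver in Protocol 6.1.4.2 covers the pregnancy test and so conflicts with the one-week window in exclusion 24

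*Protocol*

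**What the plan says.** Protocol 6.1.4.2 has a block headed "Required within 7 days prior to procedure". It contains "Complete Blood Cell Count (CBC): RBC, WBC, hemoglobin, hematocrit, platelet", then "Creatinine, BUN", the creatinine clearance formula and, as its last item, the pregnancy test where applicable. The sentence directly below covers a subject who had a non-target PCI after angiography but could not go straight on to target PCI: "the subject may be enrolled within 30 days of the initial screening without repeating the above tests". A later block in the same section lists what must be redone in the 24 hours before a delayed enrollment: ECG, angina status and cardiac enzymes. The pregnancy test is not in it.

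Table 3 schedules the pregnancy test at screening only. Note 1, attached to that column, says that subjects who had angiography but cannot proceed directly "can be enrolled within 30 days of the initial screening without reconsenting the patient and repeating screening procedures unless clinically indicated". Section 6.1.4.1 gives the same permission with the same proviso.

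Exclusion 24 (synopsis and 6.3.2.1) says that women of childbearing potential "must have a negative pregnancy test within one week before treatment". Section 6.3.2 requires every exclusion to be absent. Section 6.3.4 counts a patient as enrolled only after, among other steps, she has "met all general and angiographic eligibility criteria". SAP 6.3 lists among major violations the enrollment of a patient "who did not meet all of the inclusion or exclusion criteria".

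**The concern.** The visit section that a site works from permits something that a binding exclusion criterion does not. A coordinator who follows 6.1.4.2 for a staged case could enroll a woman on a pregnancy test up to 30 days old and believe that the file is in order. A monitor who checks exclusion 24 would record an eligibility failure.

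Two things are at stake. The first is subject protection: the one-week test is the stated safeguard against implanting a drug-eluting stent during pregnancy. The second is a clean eligibility record: a subject enrolled in line with one section of the protocol becomes a major violation under another and leaves the per-protocol set, on which SAP 15.1.3 repeats the primary analysis.

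The three statements of the waiver also differ, so it is unclear who may use it and whether a clinical reason to repeat a test limits it.

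**Working it through.** The plan gives no figure to reproduce. The check sets the passages side by side and compares two time windows.

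**Inputs**
- Normal window for the pregnancy test: 7 days before the procedure (Protocol 6.1.4.2).
- Waiver window: 30 days from initial screening (6.1.4.2, 6.1.4.1, Table 3 note 1).
- Exclusion 24 window: one week, which is 7 days, before treatment (6.3.2.1).
- Meaning of treatment: Protocol 6.2.1 identifies the single treatment as implantation of the study stent at the baseline procedure. The clock in exclusion 24 therefore runs to the target PCI and not to the earlier non-target PCI.

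**Step 1: is the pregnancy test inside the waiver?** Yes. In 6.1.4.2 it is the last item on the list that the waiver sentence refers back to. In Table 3 it is a screening procedure, and note 1 lifts the repetition of screening procedures. No place that lists mandatory repeats includes it.

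**Step 2: when can the two rules collide?** Assume that the test is drawn on the day of initial screening and is not repeated.
- Enrollment on or before day 7: test age is at most 7 days, and both rules are met.
- Enrollment from day 8 to day 30: test age exceeds 7 days, the waiver is met and exclusion 24 is not.
- Length of the conflict: 30 - 7 = 23 days.

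Section 6.1.4.2 also accepts results already available from routine care. If such a test was drawn 7 days before the first procedure and that procedure fell on the day of initial screening, its age at enrollment could reach 30 + 7 = 37 days. The oldest permitted test is therefore 30 to 37 days, depending on that assumption.

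**Step 3: what follows in the analysis?** Section 6.3.2 makes the exclusion binding, so a subject enrolled on an out-of-window test has not met all criteria. SAP 6.3 removes her from the per-protocol set. SAP 6.2 keeps subjects with major deviations in the full analysis set, so the primary analysis population does not change.

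**Step 4: do the three waiver statements agree?** No.
- Trigger: 6.1.4.2 requires that a non-target PCI was done. Section 6.1.4.1 and Table 3 note 1 cover any subject who had angiography and could not proceed directly to enrollment.
- Qualifier: 6.1.4.1 and Table 3 note 1 make an exception where a repeat is clinically indicated. Section 6.1.4.2 does not.

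**Step 5: exclusions 10 to 13.** The blood count and creatinine that feed these criteria are under the same waiver, which in 6.1.4.2 applies only when a PCI has intervened. The criteria give thresholds for creatinine clearance, hemoglobin, platelets and white cells, but no sample date. Using the screening sample contradicts no stated window. The plan simply does not say which sample decides.

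**The case against.** The waiver is permissive. It says that a subject may be enrolled without repeat tests; it does not forbid repeating them. A site that repeats the pregnancy test satisfies both rules on every day up to day 30. Since 6.3.2 and 6.3.4 require all criteria to be met, the waiver can be read as relaxing re-testing and not eligibility. This stands against one tempting inference, that the waiver overrides exclusion 24. The protocol sets no order of precedence between the two. It does not remove the conflict, because a site that uses the permission exactly as written can still breach the exclusion. The clinical-indication proviso does not cure it either: it leaves repetition to judgement and is missing from 6.1.4.2. Exclusion 25 asks for contraception from screening, which lowers the risk of pregnancy but does not satisfy a test window.

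A reader might also infer that the waiver contradicts exclusions 10 to 13, and that a subject whose values fell after the first PCI is a per-protocol violation under one section but not under another. The documents do not support this. Those criteria carry no sample date. A known fall below a limit bars enrollment whichever section is read, and an unknown one leaves no violation on the recorded data. Part of the bleeding scenario is already covered. A non-target PCI from 24 hours to 30 days beforehand must have been free of TIMI major and BARC type 3 bleeding, and exclusions 15 and 16 bar active bleeding and recent bleeding that needed attention.

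Nor do the documents support any count of affected subjects. They give neither the share of staged entries nor the number of women of childbearing potential.

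**Conclusion.** The conflict over the pregnancy test is real and should be corrected. It is narrow: it arises only for a woman of childbearing potential, enrolled under the waiver, whose test is more than 7 days old at implantation and was not repeated. With the test drawn on the screening day, that is up to 23 of the 30 permitted days. Each such case is a breach of exclusion 24 and a major violation under SAP 6.3.

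Few subjects are likely to be affected, and no effect on the 12-month target lesion failure comparison is shown. The case rests on subject protection and on an eligibility record that gives one answer.

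The differing trigger and qualifier are a lesser inconsistency in the same text. For exclusions 10 to 13 there is a gap, not a contradiction.

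**What to change.** Reconcile Protocol 6.1.4.2, 6.1.4.1 and Table 3 note 1 with exclusion 24, so that the waiver cannot be used in a way that breaches the exclusion. In the same edit, state the waiver with one trigger and one qualifier in all three places.

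As a secondary item, state which sample governs exclusions 10 to 13 when a PCI has taken place between screening and enrollment. The choice of rule is the sponsor's; the request is that it be written down once and consistently.

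The cost is a wording amendment. Any repeat pregnancy test within the one-week window is a test that exclusion 24 already demands.

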6.1.4.3 Baseline Procedure

- Angiographic eligibility criteria
- Enrollment and study stent information
- Target lesion location
- Non-target vessel treatment, if applicable
- Anticoagulation administration
- Procedural complications

- Per-protocol DAPT medications
- Adverse events

6.1.4.4 **Post-Procedure and Discharge**

- 12 lead ECG
- Angina status
- All adverse events, including related laboratory tests results and details of any subsequent repeat coronary angiography and results of such, if applicable
- Per-protocol DAPT medications
- Concomitant cardiac medication by category
- CK and CK-MB or Troponin (I or T). Two post-PCI measures are recommended, but if early discharge is contemplated, at least one post procedure measurement 6-10 hours post-PCI is mandatory with the results known before discharge. The need for further cardiac biomarker measurement will be determined by the biomarker level as detailed in Table 4 below:

Biomarker Level	Patient Status	Action
<uln ck-mb
or Troponin* <7X ULN and</uln>	Clinically stable	The patient may be discharged without additional levels.
1-3x ULN CK- MB or Troponin* 7-20X ULN and	Clinically stable	The patient may be discharged but a second level is required at 12-18 hours. If the patient had an elevated troponin level immediately prior to study PCI and post- PCI level is lower than the immediate pre-PCI level, a second level is not required.
≥3x ULN CK- MB or Troponin* >20 X ULN and/or	Not clinically stable	The patient may not be discharged until serial CK-MB or Troponin levels are decreasing AND the patient is stable. If the patient had an elevated troponin level immediately prior to study PCI and post-PCI level is lower than the immediate pre-PCI level, a second level is not required.

Table 4: Patient Status as Indicated by Biomarker Levels post-PCI

*using conventional or hs-troponin assays with 99th percentile cutoff of 8.6 ng/L to 70 ng/L

6.1.4.5 30 Days (± 7 days) and 6 Months (± 30 days) Follow-up (in clinic or telephone visit)

- Angina status
- All adverse events including related laboratory tests results, ECGs, details of any subsequent myocardial infarction, hospitalization, or repeat coronary angiography and results of such, if applicable

- Details of any subsequent coronary interventions (e.g., repeat PCI or CABG)
- Compliance to protocol-required DAPT medications
- Use and changes in chronic antiplatelet medication regimen. Data are collected for the duration of the trial
- Concomitant cardiac medication by category

6.1.4.6 1 year (- 30 Days / + 14 Days) Follow-up (in-clinic)

- Angina status
- All adverse events including related laboratory tests results, ECGs, details of any subsequent myocardial infarction, hospitalization, or repeat coronary angiography and results of such, if applicable
- Details of any subsequent coronary interventions (e.g., repeat PCI or CABG)
- Compliance to protocol-required DAPT medications
- Use and changes in chronic antiplatelet medications. Data are collected for the duration of the trial
- Concomitant cardiac medication by category
- 12 Lead ECG

Note: For subjects who refuse or cannot return to clinic for the 1 year visit, a telephone visit may be conducted in lieu of an in-clinic visit.

6.1.4.7 2, 3, 4, and 5 Year (± 60 days) Follow-up (in clinic or telephone visit)

- Angina status
- All adverse events including related laboratory tests results, ECGs, details of any subsequent myocardial infarction, hospitalization, or repeat coronary angiography and results of such, if applicable
- Details of any subsequent coronary interventions (e.g. repeat PCI or CABG)
- Use and changes in chronic antiplatelet medications. Data are collected for the duration of the trial
- Concomitant cardiac medication by category

